6.5. Dose Modification

Every effort should be made to administer study intervention on the planned dose and schedule. In the event of significant toxicity, which may include a DLT, dosing may be delayed, reduced, or discontinued as described below. In the event of multiple toxicities, dose modification should be based on the worst toxicity observed. Participants are to be instructed to notify investigators at the first occurrence of any adverse symptom. In addition to dose modifications, investigators are encouraged to employ best supportive care according to local institutional clinical practices.

Toxicities potentially related to PF-07260437 should be managed according to the dose modifications described in [Table 10](#) and [Table 11](#).

Selected toxicities that do not resolve or worsen following supportive care and dose modifications and with a clinical presentation consistent with a potential irAE without a clear alternative explanation, may require treatment with corticosteroids or other immunosuppressants and should be managed according to the management of irAEs as described in [Section 10.3.5](#).

CRS should be managed according to the CRS Mitigation and Management guidance as described in [Appendix 11](#).

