6.5.1. Dosing Interruptions

With respect to study intervention, participants experiencing Grade 3 or 4 potentially treatment-related toxicity or intolerable Grade 2 toxicity despite supportive treatment should have their treatment interrupted as indicated in [Table 10](#) and [Table 11](#).

Appropriate follow-up assessments should be done until adequate recovery occurs as assessed by the investigator. Criteria required before treatment can resume are described in [Section 6.5.2](#).

Doses may be held up to 4 weeks until toxicity resolution. Depending on when the AE resolved, a treatment interruption may lead to the participant missing subsequent planned doses within that same cycle or to delay the initiation of the subsequent cycle as follows:

- If the planned Day 1 dose (of any cycle) cannot be administered due to an AE, then Day 1 dose will be delayed until the AE has resolved and the study drug can be administered.
- If the planned Day 15 dose (of any cycle) is delayed for ≤ 7 days, then the planned day 15 dose can be administered as the delayed Day 15 dose. Day 1 of the subsequent cycle will be administered 2 weeks after the delayed Day 15 dose.
- If the planned Day 15 dose (of any cycle) is delayed for >7 days, then Day 15 will be skipped. The next dose will be administered when the AE has resolved and will be considered the Day 1 dose of the subsequent cycle.

The need for a dose reduction at the time of treatment resumption should be based on the criteria defined in the [Dose Reductions section](#), unless expressly agreed otherwise following discussion between the investigator and the sponsor.

In the event of a treatment interruption for reasons other than treatment-related toxicity (eg, elective surgery) lasting >4 weeks, treatment resumption will be decided in consultation with the sponsor.

See [Appendix 8, Section 10.8.4](#) for COVID-19 related dose interruption.

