6.5.2. Dose Delays

Re-treatment following treatment interruption for treatment-related toxicity or at the start of any new cycle may not occur until all of the following parameters have been met:

- ANC $\geq 1,000/\text{mm}^3$.
- Platelets count $\geq 50,000/\text{mm}^3$.

Nonhematologic toxicities have returned to baseline or Grade ≤ 1 severity (or, at the investigator's discretion, Grade ≤ 2 if not considered a safety risk for the participant).

If a treatment delay results from worsening of hematologic or biochemical parameters, the frequency of relevant blood tests should be increased as clinically indicated.

If these conditions are met within 4 weeks of treatment interruption, PF-07260437 may be resumed. Refer to the Dose Reductions Section 6.5.3 for AEs requiring dose reduction at the time of treatment resumption.

If participants require discontinuation of PF-07260437 for more than 4 weeks at any time during the study, then study treatment should be permanently discontinued, unless the investigator's benefit/risk assessment suggests otherwise after discussion with the sponsor. In this situation, if a treatment interruption continues for more than 4 weeks, the day when treatment is restarted will be counted as Day 1 of the next cycle.

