Pancreatitis	Continue at the same dose level.	Withhold dose until toxicity is resolved, then reduce the dose by 1 level.	Consider discontinuation (continuation requires sponsor approval).	Permanent discontinuation of study drug for related Grade 4 adverse events of any duration.
Hematologic	Continue at the same dose level.	Continue at the same dose level.	Withhold dose until toxicity is Grade <2, or has returned to baseline, then reduce the dose by 1 level.	Withhold dose until toxicity is Grade <2, or has returned to baseline, then reduce the dose by 1 level or 2 levels or permanently discontinue at the discretion of the investigator.*

* Nausea, vomiting, or diarrhea must persist at Grade 3 or 4 despite maximal medical therapy to require dose modification.

Recommended dose modifications of study intervention for immune related toxicity are described in Table 11. Please refer to [Section 10.3.5](#) for detailed dose modification and comprehensive management of irAEs.

Table 11. Dose Modifications for Immune-Related Toxicity

Organ System	Grade 1	Grade 2	Grade 3	Grade 4
GI (Diarrhea)	Continue investigational treatment.	Withhold investigational treatment. If improves to Grade 1, resume treatment. If persists >5-7 days or recur treat as Grade 3 or 4.	Withhold investigational treatment. If improves to Grade 1 after treatment, resume investigational therapy at the same dose level or reduce the dose by 1 level at the discretion of the investigator.	Discontinue investigational treatment.
Skin (Dermatitis)	Continue investigational treatment. If persists >1-2 weeks, withhold. If improves after treatment with corticosteroids, then resume investigational treatment.	Continue investigational treatment. If persists >1-2 weeks, withhold. If improves after treatment with corticosteroids, then resume investigational treatment.	Withhold investigational treatment. If improves to Grade 1 after treatment, resume investigational therapy.	Withhold or discontinue investigational treatment. If improves to Grade 1 after treatment, resume investigational therapy.
Lung (pneumonitis)	Consider delay of investigational treatment.	Withhold investigational treatment; re-image.	Discontinue	Discontinue

Table 11. Dose Modifications for Immune-Related Toxicity

Organ System	Grade 1	Grade 2	Grade 3	Grade 4
	Monitor	If symptoms return to baseline, then resume investigational treatment.		

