Liver (hepatitis)	Continue investigational treatment.	Withhold investigational treatment; increase monitoring of LFTs; resume investigational therapeutic if labs return to baseline. If elevations persist ≥ 5 to 7 days or worsen, treat with corticosteroids, resume investigational treatment if labs return to Grade 1 or baseline.	Discontinue	Discontinue
Endocrinopathies (hypothyroidism, hyperthyroidism, adrenal insufficiency, type 1 diabetes mellitus)	Continue investigational treatment.	Continue investigational treatment.	Withhold investigational treatment. If improves to Grade 1 after treatment, resume investigational therapy.	Discontinue

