Grade 1 Grade 1 AST or ALT >ULN to 3.0 x ULN and/or Total bilirubin >ULN to 1.5 x ULN	-Continue study treatment	-Continue liver function monitoring -If worsens: Treat as Grade 2 or 3 – 4.
Grade 2 AST or ALT >3.0 to \leq 5 x ULN and/or total bilirubin >1.5 to \leq 3 x ULN	-Withhold study treatment -Increase frequency of monitoring to every 3 days	-If returns to Grade \leq 1: Resume routine monitoring; resume study treatment. -If elevation persists >5 to 7 days or worsens: Treat as Grade 3 to 4.
Grade 3 to 4 AST or ALT >5 x ULN and/or total bilirubin >3 x ULN	-Permanently discontinue study treatment -Increase frequency of monitoring to every 1 to 2 days -1.0 to 2.0 mg/kg/day prednisone or equivalent -Add prophylactic antibiotics for opportunistic infections -Consult gastroenterologist/hepatologist -Consider obtaining MRI/CT scan of liver and liver biopsy if clinically warranted	-If returns to Grade \leq 1: Taper steroids over at least 1 month. -If does not improve in >3 to 5 days, worsens or rebounds: Add mycophenolate mofetil 1 gram (g) twice daily. -If no response within an additional 3 to 5 days, consider other immunosuppressants per local guidelines.

Renal irAEs		
Grade of Creatinine Increased (NCI-CTCAE v5.0)	Initial Management	Follow-up Management
Grade 1 Creatinine increased >ULN to 1.5 x ULN	-Continue study treatment	-Continue renal function monitoring. -If worsens: Treat as Grade 2 to 3 or 4.
Grade 2 to 3 Creatinine increased >1.5 and \leq 6 x ULN	-Withhold study treatment -Increase frequency of monitoring to every 3 days -1.0 to 2.0 mg/kg/day prednisone or equivalent. -Add prophylactic antibiotics for opportunistic infections -Consider renal biopsy	-If returns to Grade \leq 1: Taper steroids over at least 1 month, and resume study treatment following steroids taper. -If worsens: Treat as Grade 4.
Grade 4 Creatinine increased >6 x ULN	-Permanently discontinue study treatment -Monitor creatinine daily -1.0 to 2.0 mg/kg/day prednisone or equivalent. -Add prophylactic antibiotics for opportunistic infections -Consider renal biopsy -Nephrology consult	-If returns to Grade \leq 1: Taper steroids over at least 1 month.

Cardiac irAEs		
Myocarditis	Initial Management	Follow-up Management

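### Section 10.3.5 and Table 11 give opposite actions for a persistent Grade 2 hepatic immune-related event, and the 10.3.5 hepatic conditions leave out return to baseline

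*Protocol*

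**What the plan says.** **Section 10.3.5, hepatic table.** Grade 2 is AST or ALT above 3 and up to 5 x ULN, and/or total bilirubin above 1.5 and up to 3 x ULN. Drug is withheld and restarts on return to Grade 1 or lower. Otherwise: "If elevation persists >5 to 7 days or worsens: Treat as Grade 3 to 4". The Grade 3 to 4 row starts with permanent discontinuation and steroids. Its only recovery action is a taper over at least a month once the value is Grade 1 or lower.

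**Table 11, liver row.** At Grade 2, drug is withheld and restarts at baseline. If the elevation lasts 5 to 7 days or more, or worsens, the instruction is: "treat with corticosteroids, resume investigational treatment if labs return to Grade 1 or baseline". Only Grades 3 and 4 are discontinued.

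**Routing between them.**
- Section 6.5 says toxicities potentially related to the drug "should be managed according to the dose modifications described in" Tables 10 and 11.
- The same section sends potential irAEs to 10.3.5 when they may need steroids, describing them as: "Selected toxicities that do not resolve or worsen following supportive care and dose modifications".
- The lead-in to Table 11 refers the reader to 10.3.5 "for detailed dose modification and comprehensive management of irAEs".
- Section 6.5.1 adds: "Criteria required before treatment can resume are described in" Section 6.5.2. That section withholds re-treatment until the following is met: "Nonhematologic toxicities have returned to baseline or Grade" 1 or lower, or Grade 2 or lower at the investigator's discretion "if not considered a safety risk for the participant".

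**Eligibility.** Inclusion criterion 12 admits AST and ALT up to 5.0 x ULN when the tumour involves the liver.

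**The concern.** A site facing a Grade 2 hepatic irAE that has not settled in about a week finds two instructions in one protocol. One ends treatment for good. The other treats with steroids and permits re-exposure. Following either is compliance with one table and departure from the other.

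This is a first-in-human T-cell engager for which irAEs are anticipated, and there is no data monitoring committee. The looser reading re-exposes a participant after a liver event that needed steroids. The stricter reading permanently removes someone whom Table 11 would let restart.

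The second matter concerns participants who enter with raised transaminases. A condition fixed at Grade 1 or lower can stay unmet after full recovery to the level at which they were admitted, either for restarting drug or for starting the steroid taper.

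**Working it through.** The plan states no figure on this point, so the main check is a comparison of outcomes by scenario.

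| Hepatic irAE | Section 10.3.5 | Table 11 | Same outcome? |
|---|---|---|---|
| Grade 2, lasts about 5 to 7 days | Treated as Grade 3 to 4: permanent stop | Steroids, restart at Grade 1 or baseline | No, opposite |
| Worsens but stays Grade 2 | Permanent stop | Steroids, restart at Grade 1 or baseline | No, opposite |
| Rises to Grade 3 or 4 | Permanent stop | Discontinue | Yes |
| Grade 2, settles early | Restart at Grade 1 or lower | Restart at baseline | Different condition, no permanent stop in either |

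The difference is not just abbreviation in Table 11. Its Grade 2 diarrhea cell carries the same escalation to Grade 3 or 4 handling that 10.3.5 uses. The Grade 2 liver cell states a different action.

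**Baseline omission.** Inputs are the Grade 1 ceiling for AST/ALT, 3 x ULN (10.3.5); the Grade 2 ceiling, 5 x ULN (10.3.5); and the admitted maximum with liver involvement, 5.0 x ULN (inclusion 12). For a baseline b between 3 and 5 x ULN:

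- Fall below own baseline needed to reach Grade 1 = 1 − 3/b.
- Room to rise while staying Grade 2 = 5/b − 1.

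| b (x ULN) | Fall needed | Room to rise within Grade 2 |
|---|---|---|
| 3.0 | 1 − 3/3.0 = 0% | not needed |
| 4.0 | 1 − 3/4.0 = 25% | 5/4.0 − 1 = 25% |
| 5.0 | 1 − 3/5.0 = 40% | 5/5.0 − 1 = 0% |

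Restart appears only in the Grade 2 row, so its gap applies only to events that stay at or below 5 x ULN. At b = 5.0 any AST/ALT rise is already Grade 3 and a permanent stop in both tables. The 40% figure therefore applies only to the taper condition in the Grade 3 to 4 row. As b approaches 5, the room for an event that stays Grade 2 shrinks to nothing. Baselines at or below 3 x ULN have no gap.

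Other parts of the protocol do accept baseline: Table 11 and Section 6.5.2 for restart, and the Grade 3 irAE rule in Section 4.3.6.2 for DLT classification. Section 4.3.6.2 also expressly provides for participants with Grade 2 transaminases at baseline.

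**The case against.** The best reply is that the routing already settles the matter. Section 6.5 first gives the general instruction to use Tables 10 and 11. It then sends to 10.3.5 the very events in dispute: potential irAEs that fail to resolve, or worsen, and may need steroids. Table 11 is introduced as recommended modifications, with 10.3.5 supplying the detail. Read in sequence, a persistent Grade 2 hepatic irAE goes to 10.3.5. This stands as the better reading, and it decides the default fix. It does not remove the conflict. A pointer to further detail does not tell a site to disregard an explicit restart instruction in the table it was told to follow.

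A reader might infer that Section 6.5.2 is a third competing rule because it accepts baseline and, at discretion, Grade 2. It is not. It sets minimum conditions before re-treatment, and a stricter organ-specific stop is compatible with it.

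A reader might also infer that the 4-week limit in Section 6.5.2 rules out restart after a long steroid taper. It does not, because that section allows an exception on the investigator's benefit/risk assessment after discussion with the sponsor.

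Section 8 calls for safety issues to be discussed with the sponsor at once. That limits divergence between sites but supplies no rule for the discussion to apply.

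On baseline, the protocol partly covers the gap elsewhere: Table 11 and Section 6.5.2 for restart, baseline-adjusted liver thresholds in Appendix 6, and the exclusion of stable pre-existing conditions from the AE definition in Section 10.3.1. None of these repairs the 10.3.5 taper condition, or says that a value back at baseline has stopped persisting. The taper case does arise only after drug has been stopped, with specialist consultation called for.

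**Conclusion.** The conflict is real and narrow. It covers hepatic irAEs that stay within Grade 2 and either persist about 5 to 7 days or worsen. For those, the two sources give a permanent stop and a permitted restart respectively, and no sentence ranks them. It would be wrong to infer that the protocol is neutral between them, since the routing favours 10.3.5. It would also be wrong to extend the conflict to Grade 3 or above, where both stop treatment.

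The baseline omission is secondary. It affects participants entering with AST/ALT above 3 and up to 5 x ULN from liver involvement, for example a required 25% fall from 4.0 x ULN. A reader might infer that restart can require a 40% fall, but that figure holds only for the taper condition. No bilirubin figure is offered, because inclusion 12 sets no upper limit for participants with Gilbert's syndrome.

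The documents give no incidence for either case, so the number of participants affected is unknown. The point should be corrected because it concerns liver safety and the remedy is cheap. It does not undermine the design.

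**What to change.** 1. **Make the Grade 2 action identical** for persistence or worsening in the Table 11 liver cell and the 10.3.5 hepatic table. The default is to bring Table 11 into line with 10.3.5, that is, permanent discontinuation. If the sponsor prefers steroids with restart, say so in both places. Allow restart only at Grade 1 or lower, or baseline, and only after the steroid taper, under the existing benefit/risk exception to the 4-week limit in Section 6.5.2. Grade 3 or above stays a permanent stop either way.

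2. **Add baseline to the 10.3.5 hepatic table.** In the Grade 2 and Grade 3 to 4 rows, extend the recovery condition to Grade 1 or lower, *or to baseline if baseline was above Grade 1*. State that a value back at baseline is not a persisting elevation. SAP Section 3.4 already defines laboratory baseline as the last measurement before the first dose.

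3. **Do not yet add a blanket sentence that 10.3.5 governs.** Other rows differ, and not all in the same direction:
   - Grade 4 skin: 10.3.5 is stricter.
   - Grade 4 endocrine: 10.3.5 is more lenient, withholding and resuming where Table 11 discontinues.
   - Grade 2 pneumonitis: Table 11 restarts at baseline; 10.3.5 requires Grade 1 or lower and a completed taper.
   - Recurrent Grade 3 diarrhea and skin: a permanent stop in 10.3.5, with no recurrence rule in Table 11.

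   Reconcile these first. Until a row is reconciled, state that the stricter instruction applies.

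The cost is a few lines for the liver wording and a row-by-row check of the two tables. No visits, tests or participants are added.

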10.4. Appendix 4: Contraceptive and Barrier Guidance

10.4.1. Male Participant Reproductive Inclusion Criteria

Male participants are eligible to participate if they agree to the following requirements during the intervention period and for at least 165 days after the last dose of study intervention, which corresponds to the time needed to eliminate reproductive safety risk of the study intervention(s) plus an additional 90 days (a spermatogenesis cycle):

- Refrain from donating sperm.

PLUS either:

- Be abstinent from heterosexual intercourse as their preferred and usual lifestyle (abstinent on a long-term and persistent basis) and agree to remain abstinent.

OR

- Must agree to use contraception/barrier as detailed below.
 - Agree to use a male condom when engaging in any activity that allows for passage of ejaculate to another person.
 - Male participants should be advised of the benefit for a female partner to use a highly effective method of contraception, as a condom may break or leak when having sexual intercourse with a WOCBP who is not currently pregnant.

10.4.2. Female Participant Reproductive Inclusion Criteria

A female participant is eligible to participate if she is not pregnant or breastfeeding, and at least 1 of the following conditions applies:

- Is not a WOCBP (see definitions below in [Appendix 4, Section 10.4.3](#)).

OR

- Is a WOCBP and using a contraceptive method that is highly effective (with a failure rate of <1% per year), preferably with low user dependency, as described below during the intervention period and for at least 4 months after the last dose of study intervention, which corresponds to the time needed to eliminate any reproductive safety risk of the study intervention(s). As for participants using a highly effective method that is user dependent, this contraception method must be used together with a second effective method of contraception, as described below. The investigator should evaluate the effectiveness of the contraceptive method in relationship to the first dose of study intervention.

A WOCBP agrees not to donate eggs (ova, oocytes) for the purpose of reproduction during this period. The investigator should evaluate the effectiveness of the contraceptive method in relationship to the first dose of study intervention.

The investigator is responsible for review of medical history, menstrual history, and recent sexual activity to decrease the risk for inclusion of a woman with an early undetected pregnancy.

10.4.3. Woman of Childbearing and Non-Childbearing Potential

A woman is considered fertile following menarche and until becoming postmenopausal unless permanently sterile (see below).

If fertility is unclear (eg, amenorrhea in adolescents or athletes) and a menstrual cycle cannot be confirmed before the first dose of study intervention, additional evaluation should be considered.

Women in the following categories are not considered WOCBP:

1. Premenopausal female with 1 of the following:
 - Documented hysterectomy;
 - Documented bilateral salpingectomy;
 - Documented bilateral oophorectomy.

For individuals with permanent infertility due to an alternate medical cause other than the above, (eg, mullerian agenesis, androgen insensitivity), investigator discretion should be applied to determining study entry.

Note: Documentation for any of the above categories can come from the site personnel's review of the participant's medical records, medical examination, or medical history interview. The method of documentation should be recorded in the participant's medical record for the study.

2. Postmenopausal female:
 - A postmenopausal state is defined as no menses for 12 months without an alternative medical cause. In addition,
 - A high FSH level in the postmenopausal range must be used to confirm a postmenopausal state in women under 60 years of age and not using hormonal contraception or HRT.
 - A female on HRT and whose menopausal status is in doubt will be required to use one of the nonestrogen hormonal highly effective contraception methods if they

wish to continue their HRT during the study. Otherwise, they must discontinue HRT to allow confirmation of postmenopausal status before study enrollment.

10.4.4. Contraception Methods

Contraceptive use by men or women should be consistent with local availability/regulations regarding the use of contraceptive methods for those participating in clinical trials.

Highly Effective Methods That Have Low User Dependency

1. Implantable progestogen-only hormone contraception associated with inhibition of ovulation.
2. Intrauterine device.
3. Intrauterine hormone releasing system.
4. Bilateral tubal occlusion.
5. Vasectomized partner.
 - A vasectomized partner is a highly effective contraceptive method provided that the partner is the sole sexual partner of the WOCBP and the absence of sperm has been confirmed. If not, an additional highly effective method of contraception should be used. The spermatogenesis cycle is approximately 90 days.

Highly Effective Methods That Are User Dependent

6. Combined (estrogen and progestogen containing) hormonal contraception associated with inhibition of ovulation:
 - Oral;
 - Intravaginal;
 - Transdermal;
7. Progestogen-only hormone contraception associated with inhibition of ovulation:
 - Oral;
 - Injectable.
8. Sexual abstinence:
 - Sexual abstinence is considered a highly effective method only if defined as refraining from heterosexual intercourse during the entire period of risk associated with the study intervention. The reliability of sexual abstinence needs to be evaluated in relation to the duration of the study and the preferred and usual lifestyle of the participant.
 -

One of the following effective barrier methods must be used in addition to the highly effective methods listed above that are user dependent:

- Male or female condom with or without spermicide;
- Cervical cap, diaphragm, or sponge with spermicide;
- A combination of male condom with either cervical cap, diaphragm, or sponge with spermicide (double-barrier methods).

